10.3.3.3 Causality

The Investigator will determine the relationship of an AE to the study drug and will record it on the source documents and AE CRF. To ensure consistency of causality assessments, Investigators should apply the guidance in Table 10.3.3.3.1.

Relationship	Description
Not Related	Exposure to the IP has not occurred
	• OR
	• The administration of the IP and the occurrence of the AE are not reasonably related in time
	• OR
	• The AE is considered likely to be related to an etiology other than the use of the IP; that is, there are no facts, evidence, or arguments to suggest a causal relationship to the IP.
Related	• The administration of the IP and the occurrence of the AE are reasonably related in time
	AND
	• The AE could possibly be explained by factors or causes other than exposure to the IP
	OR
	• The administration of IP and the occurrence of the AE are reasonably related in time
	AND
	• The AE is more likely explained by exposure to the IP than by other factors or causes.

Factors suggestive of a causal relationship could include (but are not limited to):

- Plausible temporal relationship
- Absence of alternative explanations
- Rarity of event in a given patient or disease state
- Absence of event prior to study drug exposure
- Consistency with study product pharmacology
- Known relationship to underlying mechanism of study drug action
- Similarity to adverse reactions seen with related drug products
- Abatement of AE with discontinuation of study drug, and/or recurrence of AE with reintroduction of study drug

The investigator's assessment of causality for individual AE reports is part of the study documentation process. Regardless of the Investigator's assessment of causality for individual AE reports, the Sponsor will promptly evaluate all reported SAEs against cumulative product experience to identify and expeditiously communicate possible new safety findings to investigators and applicable regulatory authorities.

10.4 Procedures for Recording Adverse Events

10.4.1 Recording Adverse Events on a eCRF

Investigators should use precise medical terminology when recording AEs or SAEs on the AE eCRF. Avoid colloquialisms and abbreviations.

Record only one diagnosis, sign, or symptom per event field on the AE eCRF (eg, nausea and vomiting should not be recorded in the same entry, but as 2 separate entries).

In order to classify AEs and diseases, preferred terms will be assigned by the Sponsor to the original terms entered on the AE eCRF, using MedDRA (Medical Dictionary for Regulatory Activities) terminology.

10.4.1.1 Diagnosis versus Signs and Symptoms

Using accepted medical terminology, enter the diagnosis (if known). If not known, enter sign(s) and/or symptom(s). If a diagnosis subsequently becomes available, then this diagnosis should be entered on the AE (or SAE, as appropriate) eCRF, replacing the original entries where appropriate.

10.4.1.2 Adverse Events Occurring Secondary to Other Events

In general, AEs occurring secondary to other events (eg, cascade events) should be identified by their primary cause. For example, if severe diarrhea is known to have resulted in dehydration, it is sufficient to record only diarrhea as an AE or SAE on the AE eCRF. However, medically important events that may be linked and/or separated in time should be recorded as independent events on the AE eCRF. For example, if severe haemorrhage leads to renal failure, both events should be recorded separately on the AE eCRF.

10.4.1.3 Persistent or Recurrent Adverse Events

A persistent AE (duration of adverse event > 7 days) is one that extends continuously, without resolution, between subject evaluation time points. Events that change in severity necessitate the recording of an additional AE. AEs that do not have a change in severity should be recorded only once on the eCRF.

A recurrent AE is one that occurs and resolves between subject evaluation time points, but then subsequently recurs. All recurrences of the AE should be recorded on the AE eCRF.

10.4.1.4 Abnormal Laboratory Values

Laboratory test results will be recorded on the laboratory results pages of the AE eCRF, or appear on electronically produced laboratory reports submitted directly from the central laboratory, if applicable.

Any laboratory result abnormality fulfilling the criteria for a SAE or EOSI should be reported as such, and recorded in the AE eCRF. Any laboratory result abnormality of CTCAE Grade 4 or 5 should be recorded as an SAE in the AE eCRF.

A clinical laboratory abnormality is considered clinically significant and should be documented as an AE if not refuted by a repeat test to confirm the abnormality and **any** one or more of the following conditions is met:

- Accompanied by clinical symptoms
- Requiring a change in concomitant therapy (eg, addition of, interruption of, discontinuation of, or any other change in a concomitant medication, therapy or treatment).
- The abnormality suggests a disease and/or organ toxicity
- The abnormality is of a degree that requires active management (eg, change of dose, discontinuation of study drug, more frequent follow-up assessments, further diagnostic investigation, etc.)

This applies to any protocol and non-protocol specified safety and efficacy laboratory result from tests performed after the first dose of study medication that falls outside the laboratory reference range and meets the clinical significance criteria.

This does not apply to any abnormal laboratory result that falls outside the laboratory reference range but that does not meet the clinical significance criteria (these will be analyzed and reported as laboratory abnormalities), those that are considered AEs of the type explicitly exempted by the protocol, or those which are a result of an AE that has already been reported.

For purposes of this study, laboratory tests showing a decreased level of hFVIII activity should not be reported as adverse events unless signs of worsening are observed.

10.4.1.5 Pre-existing Conditions

A pre-existing condition is one that is present prior to administration of BMN 270. Such conditions should be recorded as medical history on the appropriate eCRF.

Proprietary and Confidential

A pre-existing condition should be recorded as an AE or SAE during the study **only** if the frequency, intensity, or character of the condition worsens during the study period. It is important to convey the concept that a pre-existing condition has changed by including applicable language in the verbatim description of the event (eg, *more frequent* headaches).

10.4.1.6 General Physical Examination Findings

At screening, any clinically significant abnormality should be recorded as a pre-existing condition (refer to Section 10.4.1.5). During the study, any new clinically significant findings and/or abnormalities discovered on physical examination that meet the definition of an AE (or an SAE) must be recorded and document as an AE or SAE on the AE eCRF.

10.4.1.7 Hospitalization, Prolonged Hospitalization, or Surgery

Any AE that results in hospitalization or prolonged hospitalization should be documented and reported as an SAE unless specifically instructed otherwise in this protocol (refer to Section 10.1.1.1).

There are some hospitalization scenarios that do not require reporting as an SAE when there is no occurrence of an AE. These scenarios include planned hospitalizations or prolonged hospitalizations to:

- Perform a protocol-mandated efficacy measurement
- Undergo a diagnostic or elective surgical procedure for a pre-existing medical condition that has not changed
- Insert an in-dwelling IV catheter (such as a Port-a-Cath or other brand) for administration of study drug or FVIII replacement therapy.
- Receive scheduled therapy (study drug or otherwise) for the study indication

10.4.1.8 Deaths

All deaths that occur during the AE reporting period (refer to Section 10.3.1), regardless of attribution, will be recorded on the AE eCRF and expeditiously reported to the Sponsor as an SAE.

When recording a death, the event or condition that caused or contributed to the fatal outcome should be recorded as the single medical concept on the eCRF. If the cause of death is unknown and cannot be ascertained at the time of reporting, record "Unexplained Death" or "Death of Unknown Cause" on the AE eCRF.

10.4.1.9 Pregnancy

Although not an AE per se, pregnancy in the partner of a subject taking trial medication should be reported expeditiously to the Sponsor to facilitate outcome monitoring by the Sponsor. Pregnancy in partner should be reported during the period up to 5 years after viral infusion.

Pregnancy in a partner should be reported within 24 hours of the site becoming aware of the pregnancy by entering the information on the Pregnancy eCRF and submitting to BPV within 24 hours of the site becoming aware of the event. The Investigator must make every effort to follow the subject's partner (with that partner's consent) through resolution of the pregnancy (delivery or termination) and to report the resolution on the Pregnancy Follow-up eCRF. In the event of pregnancy in the partner of a study subject, the Investigator should make every reasonable attempt to obtain the woman's consent for release of protected health information.

Abortion, whether therapeutic or spontaneous, should always be classified as an SAE (as the Sponsor considers these to be medically significant), recorded on the AE eCRF, and expeditiously reported to the Sponsor as an SAE.

10.5 Reporting Requirements

10.5.1 Expedited Reporting Requirements

All SAEs and EOSI that occur during the course of the AE Reporting Period (refer to Section 10.3.1), whether or not considered related to study drug, must be reported by entering the information in the AE eCRF and submitting to BPV within 24 hours of the site becoming aware of the event. Investigators should not wait to collect information that fully documents the event before notifying BPV of an SAE. BioMarin may be required to report certain SAEs to regulatory authorities within 7 calendar days of being notified about the event; therefore, it is important that Investigators submit any information requested by BioMarin as soon as it becomes available.

The Sponsor is responsible for identifying, preparing and reporting all SUSARs to the relevant competent authorities, ethics committees and investigators in accordance with the requirements identified in the Clinical Trials Regulations.

If the EDC is unavailable, all SAEs should be reported to BPV by completing the SAE Report Form and faxing or emailing the completed form to BPV within 24 hours of the site becoming aware of the event. Once the EDC is available, the information should be entered in the AE eCRF.

270-201 Amendment 7

10.5.2 Ethics Committee Reporting Requirements

Reporting of SAEs to the Independent Ethics Committee (IEC) will be done in compliance with the standard operating procedures and policies of the IEC and with applicable regulatory requirements. Adequate documentation must be obtained by BioMarin showing that the IEC was properly and promptly notified as required.

10.6 Follow-up of Subjects after Adverse Events

The Investigator should follow all unresolved AEs and SAEs until the events are resolved or have stabilized, the subject is lost to follow-up, or it has been determined that the study treatment or participation is not the cause of the AE/SAE. Resolution of AEs and SAEs (with dates) should be documented on the AE eCRF and submitted to BioMarin Pharmacovigilance and in the subject's medical record to facilitate source data verification.

For some SAEs, the Sponsor may follow up by telephone, fax, electronic mail, and/or a monitoring visit to obtain additional case details (eg, hospital discharge summary, consultant report, or autopsy report) deemed necessary to appropriately evaluate the SAE report.

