8 STUDY OBJECTIVES

The primary objectives of the study are:

- To assess the safety of a single intravenous administration of a recombinant AAV5 encoding human coagulation FVIII (AAV5-hFVIII-SQ) vector.
- To determine the dose of AAV5-hFVIII-SQ required to achieve expression of hFVIII at or above 5% of normal activity (≥5 IU/dL) at 16 weeks after infusion. The kinetics, duration and magnitude of AAV-mediated hFVIII activity in individuals with haemophilia A will be determined and correlated to an appropriate BMN 270 dose.

The secondary objectives of the study are:

- To describe the immune response to the hFVIII transgene product and AAV capsid proteins following systemic administration of AAV5-hFVIII-SQ
- To assess the impact of BMN 270 on the frequency of FVIII replacement therapy during the study
- To assess the impact of BMN 270 on the number of bleeding episodes requiring treatment during the study

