9.2 Discussion of Study Design, Including Choice of Control Group

Study 270-201 is designed to be a first-in-man, phase 1/2 open-label, dose escalation study in patients with severe haemophilia A. Four doses of BMN 270 will be evaluated and the dose escalation decision tree for Cohorts 1-3 is summarized in Figure 9.1.1.

The decision to escalate to the next dose level will be made based on the review of safety parameters and FVIII activity by the Sponsor and the DRB.

There will be no control group. Parameters for each subject will be compared to a pre-treatment assessment of safety (liver function) and efficacy (number of bleeds, use of replacement therapy).

As AAV based treatment always leads to anti-capsid immune response, no true control group (for example with an empty AAV) is possible.

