9.3.3.1 Study Safety Evaluation Criteria

If any of the following events occur in a subject in the study who has received BMN 270 infusion, enrollment into the trial will be put on halt to complete an extensive safety analysis per Section 9.1.

Proprietary and Confidential

- Any ALT elevation > 5x ULN for at least 2 consecutive weeks after administration of BMN 270, in the absence of a definitive alternate etiology for the increase
- The occurrence of Grade 3 or higher adverse events (excluding ALT elevation) assessed as related to study drug, including liver failure and clinical hepatitis
- The detection of neutralizing antibodies to hFVIII following BMN 270 infusion
- The detection of AAV vector DNA in the semen of a participant in 3 consecutive samples (which are at least 2 weeks apart) more than 52 weeks after BMN 270 infusion, as discussed in Section 9.7.8.6
- The occurrence of a malignancy excluding skin cancers at any point after BMN 270 infusion

If the following event occurs in a subject in the study who has received BMN 270 infusion, a DRB review and analysis of safety data will be undertaken to determine whether the enrollment into the trial will be put on halt:

• Grade 2 adverse event assessed as related to study drug that persists for at least 7 days

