9.4.7 Blinding

This is an open-label study.

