10.2.1 Events of Special Interest (EOSI)

The following EOSI need to be reported to the Sponsor within 24 hours of site awareness, irrespective of seriousness, severity or causality:

- Elevation of $ALT \ge 1.5x$ ULN, regardless of whether that triggers an initiation or modification of corticosteroid treatment
- Thromboembolic event

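### Section 10.6 lets active follow-up of an unresolved AE or SAE end on a not-caused judgement alone, so final outcome and resolution date are not secured for events judged unrelated

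*Protocol*

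**What the plan says.** The current text is Amendment 8; the sentences at issue read the same in Amendment 7.

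- **Section 10.6, first sentence.** The duty to follow an unresolved AE or SAE ends at any one of three points: resolution or stabilisation, loss to follow-up, "or it has been determined that the study treatment or participation is not the cause of the AE/SAE".
- **Section 10.6, next sentence.** "Resolution of AEs and SAEs (with dates) should be documented on the AE eCRF". No distinction is made by assessed cause.
- **Section 10.2.1.** Events of special interest (ALT at least 1.5x ULN, and thromboembolic events) go to the sponsor within 24 hours "irrespective of seriousness, severity or causality". Section 10.5.1 likewise requires expedited reporting of SAEs and events of special interest whatever their assessed relation to study drug.
- **Section 10.3.3.3.** "Regardless of the Investigator's assessment of causality for individual AE reports, the Sponsor will promptly evaluate all reported SAEs against cumulative product experience".
- **Study Safety Evaluation Criteria** (9.3.4.1 in Amendment 8, 9.3.3.1 in Amendment 7). One trigger for halting enrolment is "The occurrence of a malignancy excluding skin cancers at any point after BMN 270 infusion", with no relatedness condition.
- **Design.** "This is an open-label study" (9.4.7) and "There will be no control group" (9.2). The first primary objective is "To assess the safety of a single intravenous administration of a recombinant AAV5 encoding human coagulation FVIII (AAV5-hFVIII-SQ) vector" (Section 8).

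**The concern.** Attribution is one of the things a first-in-human, one-time gene transfer has to learn. There is no concurrent group whose event rate could later show that a cause had been misassigned, and whoever makes the call knows that every subject received the vector. If that call can also close the file, completeness of outcome data depends on the presumed cause. An early misattribution then becomes harder to revise, because the later course of the case was never collected.

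The sponsor's cumulative review of SAEs is meant to be independent of the investigator's opinion, yet it would draw on cases whose length of observation that opinion may have set. A statistical analysis plan cannot repair this: it cannot recover outcomes that were not collected, and Section 14.1.2 says that missing data will not be imputed.

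**Working it through.** The plan states no figure on this point and no arithmetic decides it, so the check is a comparison of the provisions in Amendment 8.

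1. **Logic of the stopping rule.** The end-points in the first sentence of 10.6 are alternatives. The third needs neither resolution nor stabilisation. An open event that is determined not to be caused by treatment or participation therefore meets the rule.

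2. **Who decides, and by what standard.** Section 10.6 names neither. The only standard available is Table 10.3.3.3.1, where the unrelated class includes an event that is not reasonably related in time to the infusion, or one likely to have another cause. With one infusion and about 5 years of observation, a late malignancy or thromboembolic event could be placed there on timing alone.

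3. **Duties that continue whatever the assessed cause.**
   - All AEs and SAEs are reportable for about 5 years (10.3.1).
   - They are asked about at every contact (10.3.2).
   - A change in severity needs an additional AE record (10.4.1.3).
   - Deaths in the reporting period are recorded and reported (10.4.1.8).
   - Liver tests follow the visit schedule: weekly to Week 36, every 2 weeks to Week 52, then every 4 weeks in Year 2 and every 6 weeks in Years 3-5. Treatment failures on the abbreviated schedule after Week 52 are tested every 12 weeks and at year end. Testing is at least twice weekly while ALT is at least 3x ULN.

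4. **What is left uncovered.**
   - *While the subject attends visits.* New severity grades and deaths are captured, and the ALT course is measured anyway. No scheduled assessment tracks the course of a thrombosis or a tumour. For these, resolution and its date depend on the follow-up that 10.6 allows to stop. Its second sentence asks for a date that its first sentence may have removed the means of obtaining.
   - *After the subject leaves, at Week 260 or early.* Visit questioning ends. Section 10.7 covers deaths and SAEs thought possibly related, and cancers the investigator learns of. An SAE already on file, judged unrelated and still open, falls outside the first group. The cancer sentence concerns a cancer developing, not the outcome of one already recorded. Sponsor queries under 10.6 are optional and for some SAEs only.

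5. **Can it be sized?** Only events that are both still open and judged unrelated are exposed. The documents give neither proportion. One subject out of the maximum enrolment is 1/15 = 6.7%. That shows how much one case weighs here; it does not estimate the effect of 10.6.

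**The case against.** The strongest reply is that the protocol has enough causality-neutral duties to make the stopping rule harmless. Much of that stands. Three stronger readings are tempting, and the documents do not support them.

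- **A reader might infer that worsening goes unrecorded.** Sections 10.3.1, 10.3.2 and 10.4.1.3 still require it to be elicited and recorded during the study, and 10.6 does not waive them. Missing it would be non-compliance, not something the plan permits. An ALT rise left with an unknown course is implausible while scheduled liver tests continue.
- **A reader might infer a flat contradiction, with other sections forbidding causality to matter.** Sections 10.2.1 and 10.5.1 govern reporting, 10.3.3.3 governs sponsor review, and the malignancy criterion is triggered by occurrence, which a later end to follow-up cannot undo. None sets the length of follow-up. Elsewhere the protocol does use relatedness: in the Grade 3 or higher and persistent Grade 2 triggers, and for post-study SAEs in 10.7. This is a tension.
- **A reader might infer that most AE outcomes are at risk.** Events that resolve before any such determination are unaffected. Events judged related carry no guarantee either, since their follow-up also ends at stabilisation or loss to follow-up. The related class in Table 10.3.3.3.1 is broad, taking in time-related events that other factors might explain, so a high unrelated share cannot be assumed.

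The reply does not dispose of the narrower point. None of these duties secures the final outcome and resolution date of an open SAE or thromboembolic event once it is judged unrelated, least of all after the last visit.

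**Conclusion.** The point holds in limited form. Section 10.6 makes active follow-up conditional on attribution, in tension with its own request for resolution dates, with the sponsor's causality-independent SAE review, and with causality-neutral reporting of SAEs and events of special interest.

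The exposed data are final outcome and resolution date for events judged unrelated while open. Event counts, in-study severity changes and deaths are not exposed. The events that matter most are SAEs, thromboembolic events and malignancies, and those open when a subject leaves. The number affected may be small and cannot be derived from the documents.

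The conclusion assumes that sites read the end-points in 10.6 literally and that no study manual outside the protocol overrides them. With safety a primary objective, no control group and at most 15 subjects, the change is worth making.

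**What to change.** Amend Section 10.6 so that the not-caused end-point no longer applies to SAEs, naming malignancies explicitly, or to events of special interest as defined in 10.2.1. Their outcome should be recorded until resolution, stabilisation, loss to follow-up or end of study, whatever the assessed cause. Add that the outcome status of any such event still open is recorded at the subject's last visit. The present sentence has no end-of-study limit, so the new one should be drafted so that it does not shorten follow-up already required for events judged related. Other non-serious AEs can keep the present wording.

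The cost is an amended sentence plus slightly more AE follow-up and data entry, at visits already scheduled through Week 260. This changes data capture only; no treatment or clinical management rule is touched.
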